## **15.12            Laboratory Endpoints: VIP and Inflammatory Markers**

The secondary laboratory outcome measures are VIP, TNF $\alpha$ , IL6, and other inflammatory markers as measured in the central laboratory. Mean VIP per day will be compared using a paired t-test within treatment group and using an unpaired t-test between treatment groups per day. The inflammatory markers will be evaluated for time to normalization (to be determined per endpoint prior to database lock); these endpoints will be analyzed in the same manner as VIP when treated as a continuous measure.

The mITT population will be used for the analysis. VIP and inflammatory markers are not required beyond the 165 patients enrolled mark.

## **15.13            Overall Safety Endpoints**

Standard safety analyses are planned. Adverse events will be coded in MedDRA. The incidence, severity, relationship, and worst degree will be assessed with attention paid to AEs occurring during the first three days when infusion is to be administered. The incidence of SAEs and deaths/withdrawals due to treatment will also be assessed. The following additional adverse events are of special interest:

- Diarrhea that leads to treatment discontinuation
- Renal failure
- Bleeding events
- Liver toxicity
- Hypotension/shock.

All safety results will be presented separately for each treatment group. Safety endpoints will include adverse events, vital signs (VS), and relevant clinical chemistries and hematology parameters. Safety and tolerability will be assessed using two-sided Fisher Exact tests to compare RLF-100 vs. Placebo. For each treatment group as well as for the difference, two-sided 95% confidence intervals will be computed for each system organ class and for any preferred terms with >10% incidence for either study treatment.

Mean changes from randomization baseline will be displayed for each serum chemistry and hematology parameter as well as the shift; unpaired t-tests will be used to compare RLF -100 vs. Placebo at designated study times. In addition, paired t-tests will be performed for the change from randomization baseline within each study treatment group.

The safety population will be used for these analyses.

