## 8.3 Number of Participants

Initially, randomization will result in 14 participants to receive RLF-100 + SOC and 7 participants to receive placebo + SOC in the primary efficacy cohort comprised of patients who meet enrollment criteria and have been on mechanical ventilation for <8 days (including zero days for those not on mechanical ventilation). The total number of participants may expand to 198 patients (132 drug/66 placebo) if there are acceptable efficacy and safety profiles at the interim analyses. The analysis at 21 patients will be unblinded so this cohort will not be part of the final analysis but will be included in a supportive analysis since results remain confidential. Thus, the sample size for analysis purposes will be 198 patients for the primary analysis.

[figure not shown]

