## 10.7 Enrollment

The enrollment will be in accordance with a group sequential design. Up to 12 sites will participate.

The sample size for analysis purposes will be 198 patients (132 drug/66 placebo) for the primary analysis.

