# 12. ASSESSMENT OF SAFETY

## 12.1 Serious Adverse Events

Measurement of serious adverse events (SAE) will be the basis for assessing safety of RLF-100. All SAE's will be recorded on an IRB approved SAE Report Form. The SAE Report Form will include the exact nature of the event and the circumstances of the subject at the time of the event, in addition to the usual information required to document AEs or SAEs. Data on all the above will be collected on separate eCRF pages. The latest version of the AE dictionary, MedDRA, will be used for the classification and analysis of AEs entered in the study database. For regulatory reporting, SAEs will be coded using MedDRA.

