## 14.3 Study Populations

The intent-to-treat (ITT) population will be based on all randomized patients receiving any study treatment. ITT will be analyzed as randomized.

The safety population will be based on all randomized patients receiving any study treatment. Safety will be analyzed as treated.

The modified intent-to-treat (mITT) population will exclude untreated patients as well as ineligible patients; this will be the primary efficacy population. The primary analysis set will not condition on any post-randomization outcomes.

In the event that >5% of the mITT population experience a major protocol deviation that impacts the primary efficacy endpoint, such cases will be excluded and a Per Protocol (PP) population will be constructed and the primary efficacy endpoint analyses will be repeated for the PP population. A BDRM will be held to review and to determine such major deviations which would make it difficult to evaluate the study therapy, e.g. going on an approved Critical COVID-19 therapy (none currently exist) or premature withdrawal from study. The BDRM will be conducted at study completion to determine final mITT and PP population membership.

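### Section 15.13 plans no risk-difference interval for overall SAEs, treatment-related deaths/withdrawals or the five special-interest categories as such, so the Fisher p-value leaves the size of any excess harm unstated

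*Combined protocol and SAP*

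**What the plan says.** Section 12.1 sets the priority: "Measurement of serious adverse events (SAE) will be the basis for assessing safety of RLF-100". Section 15.13 then gives the method: "Safety and tolerability will be assessed using two-sided Fisher Exact tests to compare RLF-100 vs. Placebo". The next sentence of 15.13 adds estimation, per arm and for the difference, but with a limited scope: "two-sided 95% confidence intervals will be computed for each system organ class and for any preferred terms with >10% incidence for either study treatment".

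Two other statements in 15.13 name outcomes that this scope does not mention. One is "The incidence of SAEs and deaths/withdrawals due to treatment will also be assessed". The other, "The following additional adverse events are of special interest", introduces five categories: diarrhea leading to discontinuation of treatment, renal failure, bleeding, liver toxicity, and hypotension or shock. No interval, upper bound or excess-risk threshold is attached to any of them as a category.

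On numbers, section 10.7 states: "The sample size for analysis purposes will be 198 patients (132 drug/66 placebo) for the primary analysis". Section 14.3 defines the safety set more widely: "The safety population will be based on all randomized patients receiving any study treatment". Section 8.3 says of the first 21 patients (14 and 7) that "this cohort will not be part of the final analysis but will be included in a supportive analysis". The safety denominators could thus be 132/66 or, if those patients are added, 146/73. The plan gives no background event rates, alpha or power for safety.

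**The concern.** The interval rule is organised by MedDRA level and frequency, while the outcomes the plan ranks highest are defined in other ways. An overall SAE count is neither a system organ class nor a preferred term. Diarrhea that stops treatment is a subset of a term. Bleeding, renal failure, liver toxicity and hypotension/shock can each be spread over several preferred terms, any of which may stay at or below 10%, and a system organ class mixes them with unrelated events.

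For these outcomes the comparison of incidence that 15.13 specifies is a p-value. In a trial sized for efficacy, a non-significant Fisher test is compatible with a sizeable increase in harm, and the p-value does not show how large that increase could be. At stake is how the final safety results read, not the conduct of the trial.

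**Working it through.** **Inputs.** Arms 132/66 (section 10.7), and 146/73 as the alternative (132+14 and 66+7). Two-sided Fisher test (section 15.13). The 0.05 level and all event rates are assumptions, because the plan states none for safety.

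**Plan's own figure.** There is no safety power to reproduce. The only stated power is 81% for the primary endpoint, 62% v 40% with 198 patients (section 14.5). The exact Fisher calculation used below gives 82.3% for those rates at 132/66. The plan cites a different method, so this only shows that the calculation behaves sensibly at this sample size.

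**Miss rate.** For true rates p1 (RLF-100) and p0 (placebo):

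miss = 1 − Σ Bin(x; n1, p1) · Bin(y; n0, p0),

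summed over all tables (x, y) with Fisher p ≤ 0.05 and the higher observed rate on RLF-100.

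True doubling:

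| Placebo → RLF-100 | Missed, 132/66 | Missed, 146/73 |
|---|---|---|
| 5% → 10% | 84% | 82% |
| 7.5% → 15% | 73% | 68% |
| 10% → 20% | 60% | 55.5% |
| 12.5% → 25% | 49% | 43% |
| 15% → 30% | 37% | 32% |
| 20% → 40% | 19% | 15% |
| 30% → 60% | 2% | 1% |

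At 132/66 power is 48.7% for a placebo rate of 12% and 51.1% for 12.5%, so a doubling is missed more often than not only below about 12%. At 146/73 the crossing point is slightly lower, between 10% and 12.5%.

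**Overall SAEs.** Deaths are SAEs (section 12.3), all qualifying events are reported as such (section 12.6), and section 6.2 puts mortality near 50%. A doubling is then the wrong yardstick: from 50% it would mean 100%. On the absolute scale at 132/66, from an assumed placebo rate of 50%:
- a rise to 60% is missed 75% of the time;
- a rise to 65% is missed 49% of the time.

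**What an interval adds.** Newcombe's interval combines the Wilson limits (l, u) of each arm:

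lower = d − √[(p1 − l1)² + (u0 − p0)²]; upper = d + √[(u1 − p1)² + (p0 − l0)²].

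Take observed SAEs of 79/132 (0.5985; Wilson 0.5132 to 0.6782) and 33/66 (0.5000; 0.3827 to 0.6173), so d = 0.0985:
- lower = 0.0985 − √(0.0853² + 0.1173²) = 0.0985 − 0.1450 = −0.0465;
- upper = 0.0985 + √(0.0797² + 0.1173²) = 0.0985 + 0.1418 = +0.2403.

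Fisher p = 0.22, with an interval of −4.7 to +24.0 points.

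Two examples of a single term below the 10% cut-off, which would have no interval at term level:
- 12/132 (9.1%) v 3/66 (4.5%): p = 0.39, difference +4.5 points, interval −4.3 to +11.4.
- 13/132 (9.8%) v 2/66 (3.0%): p = 0.15, difference +6.8 points, interval −1.6 to +13.5.

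**The case against.** **A reader might infer that a doubling of harm would usually be missed.** That holds only for placebo rates below about 12%. Overall SAEs should lie far above that, and renal failure or hypotension/shock may too in an ICU population. The plan gives no rates that would settle it, so the general statement is not supported.

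**A reader might infer that safety has no intervals, or that the Fisher test is the only comparison.** That is also too broad. Every system organ class and every preferred term above 10% gets an interval for the difference, so a common component of a special-interest category would have its own, and a rarer one would still fall within a class that has one. All-cause mortality, the gravest SAE, has a hazard ratio and Day 28 and Day 60 comparisons with 95% intervals (section 15.6). Days free of organ failure are compared by mean difference (section 15.8). Laboratory values are compared between arms (section 15.13).

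**A reader might infer that the plan treats p>0.05 as proof of safety.** It nowhere says so. The DSMB also reviews unblinded adverse events (section 17.2), and section 14.1 leaves full specification to an analysis plan to be finalised before database lock.

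**Intervals do not cure low power.** The miss rates come from 198 patients and would not change. Because results are shown by arm, a reader could derive the intervals from the counts.

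All of this stands, and it limits the point to reporting. It does not close the gap: none of these provisions gives an interval for overall SAEs, for treatment-attributed deaths and withdrawals, or for the five categories as defined. DSMB review serves the conduct of the trial and does not replace the final reported analysis.

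**Conclusion.** The point holds as a minor reporting weakness. For the outcomes the plan itself puts first, section 15.13 specifies a test but no estimate of how much excess harm remains possible.

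For rarer special-interest categories, with placebo rates below about 12%, the Fisher test has less than 50% power for a doubling at 132/66. For a frequent outcome such as overall SAEs, increases of 10 to 15 points from 50% would go undetected in about three quarters to one half of trials. These figures rest on assumed event rates, a 0.05 level, and arms of 132/66; with 146/73 the results for a doubling are slightly better and the conclusion is the same.

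**What to change.** In section 15.13, extend the existing interval rule. Report the risk difference (RLF-100 minus placebo) with a two-sided 95% score-type interval (Newcombe or Miettinen-Nurminen) for overall SAEs, for deaths and withdrawals due to treatment, and for each of the five special-interest categories, whatever their incidence. Add that Fisher p-values for safety are descriptive and that p>0.05 is not evidence of no increase in risk.

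This needs one or two sentences and a few table columns. It needs no new data, no change in sample size and no change in patient management. The small downside is that the safety tables will show visibly wide intervals.

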# **16.            SOURCE DATA & DOCUMENTS**

## **16.1            Sources of Research Materials**

The following source data and documents will be collected. All blood samples, except those taken for cytokine and arachidonate metabolite level monitoring, which would be part of this investigation, would be obtained in the normal course of clinical care of these patients as described above.

## **16.2            Case Report Form**

The Case Report Form (CRF) is an integral part of the study and subsequent reports. The CRF must be used to capture all study data recorded in the patient's medical record. The CRF must be kept current to reflect patient status during the study. Only a patient screening and randomization number will be used to identify the patient.

## 16.3 Patient Identification

Patient name, medical record number, age, gender, height, weight, ethnic background, residence address with zip code will be collected.

## 16.4 General Clinical Data

Primary diagnosis, coexisting diagnoses / conditions, hospital length of stay and outcome will be collected.

## 16.5 Lung Injury / ARDS Data

PaO2/FiO2 ratio; PEEP/CPAP; peak, mean & plateau pressures; compliance (dynamic and quasi-static); tidal volume; respiratory rate; minute ventilation, lung injury score, chest X-ray findings will be collected.

## 16.6 Laboratory Data

Arterial blood pH, PCO2, PO2; electrolytes (Na, K, Cl, HCO3); renal function (BUN, serum creatinine); glucose, albumin & total plasma proteins; liver function tests; blood cell count; coagulation profile; lactic acid and D-Dimer will be collected.

## 16.7 Vital Signs, Respiratory and Hemodynamic Data

Blood pressure (systolic, diastolic, mean), heart rate, respiratory rate, cardiac output/cardiac index, pulmonary artery (PA) wedge pressure, systolic, diastolic & mean pressures (if PA catheter is in place), right atrial/central venous pressure, systemic and pulmonary vascular resistance, systemic O2 delivery, daily urine output, daily fluid intake will be collected.

## 16.8 Medical Therapy Data

The therapeutic milieu for RLF100-001 – ICU-type settings during the COVID-19 pandemic – requires a thoughtful and practical approach to the capture of concomitant medications in clinical studies. Specifically, the capture of relevant concomitant medications is required under three circumstances:

1. As part of a relevant medical history entry, where relevant medical history is defined as relating to an inclusion or exclusion criteria;
2. As part of an AE entry, for agents administered in response to the AE; and
3. Agents of interest, namely Biotin, IL6, antiviral therapies, steroids, nitric oxide, epoprostenol (Flolan), pressors (e.g., norepinephrine, epinephrine, Vasopressin), paralytics, anticoagulants, convalescent plasma, and tocilizumab (Actemra) and other immunomodulators.

Please note there is a unique dedicated CRF page for capturing concomitant use of convalescent plasma – no need for a duplicate entry on a concomitant medication form.

Furthermore, sites will be asked to report unusual circumstances in their ICU that require medical therapy that can negatively affect the prognosis of a patient, e.g. emergence of treatment resistant bacteria leading to high mortality.

## 16.9 Pharmacokinetic Sampling

The pharmacokinetics of intravenous Aviptadil are well understood and do not require revalidation in this study.

## 16.10 Blood Sampling

Blood samples are obtained for biochemical, electrolyte, and hematologic profiles per ICU protocol. Blood samples for cytokine (TNF-alpha, IL-6, which correlate with the inflammatory response are obtained before infusion, during infusion, and at 12 hours, and then daily on day 5, day 7 and day 28 or day of

discharge. Leukotrine E4 (urine) and Plasma VIP levels are checked at the same intervals to ensure the delivery of the peptide into the circulation. Plasma is separated within 30 min, frozen and stored at -70 C until the assays are performed, by specific radio-immunoassays or ELISA. Additionally, D-Dimer may be added when available. The procedures for blood samples for cytokines, leukotrine E4 urine and VIP plasma are not required after enrollment of the 165th evaluable patient.

## LABORATORY VISIT SCHEDULE FOR PROTOCOL RLF100-001

NeuroRx, Inc.

VISIT NAME	DAY1/DAY2/DAY3	DAY5/DAY7/EOS
VISIT TYPE (RQ=Required, Opt=Optional, U=Unscheduled)	U	U
OCCURRENCE	-	-
KIT TYPE	T-1	T-2
Group Name(s)		Specimen Type
CYTOKINES	Serum	X
CYTOKINES PRE	Serum	X
CYTOKINES 2HR	Serum	X
CYTOKINES 12HR	Serum	X
Service(s)		
VASOACTIVE INTSTNL POLYPEPTIDE	Plasma	X
LEUKOTRIENE E4 URINE	Urine	X

X Mandatory testing

## 17. STUDY MONITORING

### 17.1 Study Monitoring

The study sites have been evaluated by the sponsor in conjunction with the CRO to determine suitability for the proposed study. Information reviewed included, but was not be limited to, facility details and site capabilities, past performance in similar studies, investigator, and staff experience, ongoing studies at the site, projected enrollment in this study, and FDA or other agency audit findings. Prior to subject enrollment, a virtual study initiation visit will be completed by video conference to ensure the following: IRB approval has been obtained and documented prior to subject screening, the investigators and study personnel are appropriately trained and clearly understand the study, the investigators and study personnel accept the obligations incurred in undertaking this clinical investigation.

Periodic remote monitoring visits will be made in accordance with the approved monitoring plan at all active study sites throughout the clinical study to assure that the investigator obligations are fulfilled, and all applicable regulations and guidelines are being followed. These visits will assure that the facilities are still compliant with study requirements, the protocol and investigational plan are being followed, the IRB has been notified of approved protocol changes as required, complete records are being maintained, appropriate and timely reports have been made to the sponsor and the IRB, and the site Investigator is executing all agreed activities. Given the public health crisis, these visits will be done via virtual means and specific monitoring arrangements with each site.

### 17.2 Data Safety and Monitoring

All results from this study will be reviewed by a Data Safety and Monitoring Committee, chaired by [name], MD, MHS, Dean Emeritus of the Bloomberg School of Public Health. Membership of this committee will include: a clinician specialist in Critical Care Medicine, a biostatistician, and a lay patient

advocate. The committee will critique the progress of the trial, carefully examine any incidents of adverse reactions, and may suggest appropriate revisions in the protocol. DSMB functions include, among others, ongoing assessment of unblinded data to determine whether any of the treatment arms show increased risk for AEs.

## 17.3 Medical Monitor

The Medical Monitor will review and approve the eligibility of all screened subjects, review all AEs, assess the benefits and risks of protocols on an ongoing basis, and work in collaboration with the IRB and DMC to identify safety signals and trends. In addition, the Medical Monitor will be available for site questions regarding inclusion/exclusion criteria, protocol conduct, and safety. Trained and qualified physicians will be available to provide coverage during times when the medical monitor is unavailable. Sites will be provided with the Medical Monitor's cell phone number for emergency situations. Otherwise, sites are instructed to contact the Medical Monitor through email. All critical conversations with sites will be documented by the Medical Monitor and reviewed periodically by the sponsor. Each month the Medical Monitor will receive a listing of protocol violations for review and identification of possible trends.

## 17.4 Audits and Inspections

Contracts with study sites will specify that sponsor or its representatives will have direct access to source data and documents for study monitoring, which may be done through virtual/electronic means.

Additionally, the IRB and FDA may review source data following appropriate guidelines for this process.

## 17.5 Institutional Review Board

The study protocol and any amendments will be reviewed by the Advarra Institutional Review Board (IRB). The IRB will review the informed consent form, their updates (if any), and any written materials given to the participants. IRB approval will be obtained and documented prior to subject enrollment and screening. Before study initiation, the investigator must have written and dated approval from the IRB for the protocol, consent form, subject recruitment materials/process (e.g., advertisements), and any other written information to be provided to subjects. The investigators will provide the IRB with reports, updates, and other information (e.g., Safety Updates, Amendments, and Administrative Letters) according to regulatory requirements and Institution procedures. A detailed list of required regulatory documents, to be submitted to the sponsor, will be sent upon final approval of the protocol.

# 18. ETHICAL CONSIDERATIONS

## 18.1 Ethical Considerations

***Anticipated benefits to participants and others:*** There are at present no satisfactory specific treatments for ARDS, or multiple organ dysfunction. Based on a large body of experimental work, there is reason to expect that RLF-100 (aviptadil) may prove effective in increasing survival rates in COVID-19 patients with ARDS, as well as increasing blood O2, reducing organ failure and reducing cytokine cascades.

***Anticipated risks to participants and others:*** The only anticipated risks are due to the side-effects noted above of hypotension, tachycardia and watery diarrhea. Aviptadil has been evaluated in 4 species toxicology studies and the LD50 is more than 50x the exposure contemplated in this trial.

## 18.2 Ethical Conduct of the Study

This study will be conducted in accordance with the ethical principles that have their origins in the Declaration of Helsinki, in compliance with the approved protocol, GCP, and applicable regulatory requirements.

## 18.3

### Informed Consent

Direct patient consent is always preferred if possible, but patients are sometimes unable to give consent in this setting. Under these circumstances, the patient's legally authorized representative (LAR) must be capable of understanding the nature of this study and its potential risks, discomforts, and benefits. Study physicians or their delegate will obtain consent after they have fully explained the study purpose and procedures, and the LAR has demonstrated an understanding of the protocol, willingness to participate, and competency to consent. The investigator or their delegate must ensure that subjects are clearly and fully informed about the purpose, potential risks, and other critical issues regarding clinical trials in which they volunteer to participate. Preparation of the site-specific consent form is the responsibility of the site Principal investigator and must include all elements required by CFR 21 Part 50.25 and the IRB.

